Deployments to austere and remote mountainous regions will occur during Multi-Domain Operations (MDO). Rapid ascent to high altitude (i.e., hypobaric hypoxia; HA) elicits physiologic and metabolic adjustments that collectively degrade physical performance and augment dietary requirements. In particular, HA exposure increases reliance on carbohydrate for fuel to sustain physical activity, resulting in rapid declines in muscle glycogen content which, in part, contributes to decreased performance (1-3). To combat declines in physical performance, the Modular Ration Enhancement Operations HA (MORE-HA) was created to provide additional dietary carbohydrate to fuel sustained physical activity. However, recent studies from our laboratory have consistently demonstrated a 30-50% reduction in oxidation of exogenous glucose consumed by unacclimatized lowlanders performing steady-state exercise during acute (< 8 hrs) high altitude (HA) exposure compared to metabolically-matched exercise performed at sea level (SL; **Figure 1**) (3, 4). Reduced exogenous glucose oxidation during acute (< 8 hrs) HA exposure has also been demonstrated by others (5-7). Across studies, reductions in exogenous glucose oxidation occurred whether exercise at SL and HA were matched for absolute (3-5) or relative (6, 7) intensity. Consistent results between investigations from multiple laboratories, matching for different exercise intensities, indicates a true physiological dysregulation in use of exogenous carbohydrate for fuel use during aerobic exercise after initial arrival to HA from SL.

Accompanying lower rates of exogenous glucose oxidation at HA are increases in circulating glucose and insulin concentrations (**Figure 2A,B**), and reductions in glucose rate of disappearance and metabolic clearance rate (MCR; **Figure 2C,D**) during steady-state exercise compared to SL (3). These data are characteristic of insulin resistance (8) and suggest that reductions in peripheral glucose uptake may be a primary factor contributing to lower rates of exogenous glucose oxidation at HA. The inability to effectively use dietary carbohydrate as a metabolic fuel source and the likelihood that peripheral insulin resistance modulates those effects, suggests that a more aggressive solution than carbohydrate supplementation alone is required to optimize fuel utilization during hypoxia and enhance physical performance during future HA MDO.

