Margolis et al. *Metabolism* 2019. Values mean \pm SD. Values with different letters are different from each other. *HA different than SL. ● Sea Level △ High Altitude

One possible solution is to employ short-term use of insulin sensitizing drugs, such as biguanides (Metformin) and thiazolidinediones (Pioglitazone; PIO), which are commonly prescribed to maintain glucose homeostasis in type II diabetics. In the context of acute HA exposure, there is evidence that Metformin may improve hypoxia-induced insulin sensitivity and increase muscle glycogen synthesis at rest (9). Though Metformin enhances insulin sensitivity and peripheral glucose uptake, it also reduces intestinal glucose absorption and hepatic gluconeogenesis. The latter effects may limit the amount of exogenous and endogenous glucose available to fuel performance. Conversely, PIO's primary mechanism of action is to target peripheral tissue (e.g., muscle and lipid), as well as the liver to improve insulin sensitivity and glucose uptake without affecting intestinal glucose absorption. The mechanism of action for PIO suggests it is more appropriate than Metformin as an insulin sensitizer to enhance glucose uptake and oxidation to sustain physical performance during unacclimatized HA exposure. To date, no study has assessed the effectiveness of PIO on improving insulin sensitivity at HA to enhance exogenous glucose oxidation or glucose turnover.

Acute High Altitude Exposure, Inflammation and Iron Status

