Rapid deployment to remote mountainous regions will occur during MDO. Unacclimatized Service members experience altered carbohydrate metabolism, causing an increased reliance on glycogen for fuel, concomitant with a blunted ability to take up and oxidize exogenous carbohydrate. These negative physiological effects likely exacerbate declines in physical performance at HA. This proposal directly supports the Military Operational Medicine Research Program's Physiological Health and Performance Program Area under the Biomedical Performance Enhancement (BPE) Work Unit. Specifically, the proposed work aligns to BPE Strategic Plan's *Technical Objective 1.1.3: Material solutions (pharmacological) that enhance Soldier resistance to environmental stressors*.

This proposal will provide guidance for use of PIO to enhance exogenous carbohydrate oxidation at HA operations, and will provide the opportunity to determine if carbohydrate supplementation can indeed enhance performance if substrate metabolic dysregulation is avoided during HA exposure. Information from this proposal would be valuable to operational partners such as USSOCOM and the 10th Mountain Division who engage in HA MDO.

B4. OBJECTIVES/SPECIFIC AIMS/RESEARCH QUESTIONS

Objective:

1. Determine the effects of PIO on exogenous glucose oxidation and glucose turnover during exercise under acute HA exposure compared to PLA.
2. Determine the effects of PIO on inflammation during acute HA exposure compared to PLA.
3. Determine the effects of PIO on markers of iron status during acute HA exposure compared to PLA.

Hypotheses:

1. Exogenous glucose oxidation, Rd, and MCR during metabolically-matched, steady-state exercise at HA will be greater after PIO administration compared to PLA.
2. Inflammation will be lower during acute HA exposure after PIO administration compared to PLA.
3. Markers of iron status will be altered during acute HA exposure after PIO administration compared to PLA.

B5. RESEARCH PLAN

B5.1 Research Design

This study will be a randomized crossover double blind placebo control trial.

Table 1: Study Timeline

Study Day	Baseline					Trial 1					Washout	Trial 2				
	SV	1	2	3	4	5	6	7	8	9		20	21	22	23	24
Medical Screening	X															
Body Composition		X														
Height		X														
Weight		X								X						X
VO ₂ peak		X	X													
High Altitude Exposure			X							X						X
Practice Exercise				X	X											
Glycogen Normalization						X							X			

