PIO/PLA						X	X	X	X	X		X	X	X	X	X
Study Diet						X	X	X	X			X	X	X	X	
Steady-State Exercise										X						X
Carbohydrate Tracer Study										X						X
Blood Sampling										X						X
Breath Sampling										X						X

Timeline may shift based on participant availability, weekend, and holiday schedules.

B5.2 Research Subjects/Population(s)

B5.2.1 Subject Population(s)

Subject population will be representative of active duty male service members, being in good health and recreationally active. Previous studies at USARIEM (Protocol# 16-02HC and 18-09H) which have evaluated metabolically-matched exercise at HA compared to SL have only been performed in male volunteers. It is apparent that sex-based differences exist during low-to-moderate intensity endurance exercise at sea level. Sex-based differences in substrate oxidation during exercise at SL may result in differences in response to change in substrate oxidation at HA between men and women. Therefore, this study will recruit male volunteers only as sex differences in glucose metabolism at HA are not known. Based on findings from this and our previous studies, a similar series of investigations will be conducted in the future to assess the impact that unacclimatized HA exposure on females.

B5.2.2 Number of Subjects, Records, and/or Specimens

To complete testing on the 8 volunteers necessary to reach statistical power, we estimate we will need to enroll 24 individuals. All screening will stop once complete data has been collected on 8 volunteers. Records and specimen collection are described in the Research Procedures and Data Collection sections. During briefings and consenting potential participants will be informed that even though they may be eligible and want to participate, if we are able to obtain enough data from preceding subjects, they may not ultimately be tested. These individuals may be recruited from the HRV population, civilians, and active duty military personnel (on and off the installation).

B5.2.3 Inclusion Criteria

- Men aged 18 – 39 years
- Born at altitudes less than 2,100 m
- Physically active (exercise minimum 2 days per week)
- Have supervisor approval (permanent party military and civilians)
- Willing to refrain from alcohol, smokeless nicotine products and dietary supplement use during study periods

B5.2.4 Exclusion Criteria

- Born at altitudes greater than 2,100 m
- Musculoskeletal injuries that compromise exercise capability

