5.7.1.3 Any device not approved by the FDA

N/A

B5.7.2 Drugs

B5.7.2.1 FDA-approved and used in accordance with the approved labeling

B5.7.2.2 FDA-approved and used in a manner not in accordance with its approved labeling
Pioglitazone, Thiazolidinedione, Takeda Pharmaceutical Company

B5.7.2.3 Any drug not approved by the FDA

N/A

B8 Statistical Analysis

B5.8.1 Sample Size Estimation

Based on results of exogenous carbohydrate oxidation and MCR rate between SL and HA in our previous investigation (3, 4), a sample size of 8 is required to achieve 80% power (**Table 4**). We will request to enroll up to 24 individuals to account for withdrawals from the study.

Table 4: Previous study effect sizes

Study	Outcome	Delta	Effect Size	Sample Size
Young et al. (4)	Exogenous Glucose Oxidation	0.35 ± 0.21	1.11	7
Margolis et al. (3)	Exogenous Glucose Oxidation	0.09 ± 0.06	0.95	8
Margolis et al. (3)	MCR	3.1 ± 2.0	0.98	7

B5.8.2 Data analysis

Statistical analyses will be conducted using either SPSS (IBM Corp. Armonk, NY), SAS 9.3 (SAS Institute Inc., Carey, NC), or equivalent. Shapiro Wilks will be used to assess all data for normality. Data that are not normally distributed will be log transformed for statistical analysis. Paired T tests will be used to assess effects of study arms (HA+PIO vs. HA+PLA) on chamber conditions (barometric pressure, temperature, and humidity), oxygen saturation, heart rate, $\dot{V}O_2$, $\dot{V}CO_2$, respiratory exchange ratio, ventilation exchange, total glucose and fat oxidation, plasma glucose, muscle, and liver oxidation. Mixed Model repeated measures ANOVA will be used to assess the effects of condition, time, and their interactions for breath ^{13}C -enrichments, exogenous glucose oxidation, and blood analytes. Bonferroni adjustments for multiple comparisons will be performed if significant interactions are observed.

SECTION C: HUMAN RESEARCH PROTECTIONS

C1. RECRUITMENT AND CONSENT

C1.1 Identification and Selection of Subjects

Volunteers will be recruited from the federally and non-federally employed civilian population, the Natick Human Research Volunteer (HRV) Pool, NSSC active duty military personnel, and the active duty population located at other military organizations, to include, but not limited to coordination with the NSSC Soldier and Squad Optimization and Integration Team (SSO-IT).

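### The 80% power for 8 completers in B5.8.1 belongs to sea level versus altitude, not to pioglitazone versus placebo at altitude, and the plan never states what drug effect 8 can detect

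*Combined protocol and SAP*

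**What the plan says.** B5.8.1 rests the sample size on exogenous carbohydrate oxidation and MCR in two earlier studies (references 3 and 4), using results "between SL and HA in our previous investigation (3, 4), a sample size of 8 is required to achieve 80% power". Table 4 lists three effects from those studies, with sample sizes of 7, 8 and 7, and the text adopts 8 for 80% power. Alpha and the number of sides are not given.

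The first hypothesis in B4 concerns a different contrast: "Exogenous glucose oxidation, Rd, and MCR during metabolically-matched, steady-state exercise at HA will be greater after PIO administration compared to PLA". B5.8.2 follows it: "Paired T tests will be used to assess effects of study arms (HA+PIO vs. HA+PLA"), with a repeated-measures mixed model for exogenous glucose oxidation.

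B5.2.2 then makes 8 the stopping point for recruitment: "To complete testing on the 8 volunteers necessary to reach statistical power", and "All screening will stop once complete data has been collected on 8 volunteers".

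On what PIO may achieve, B2 says that "no study has assessed the effectiveness of PIO on improving insulin sensitivity at HA", and that "reductions in peripheral glucose uptake may be a primary factor contributing to lower rates of exogenous glucose oxidation at HA".

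**The concern.** A power statement is tied to a contrast and to an effect size on that contrast. The sea-level-minus-altitude difference (SL-HA) equals the PIO-minus-PLA difference only if the drug removes the whole altitude deficit. The protocol gives no expected PIO-PLA difference, no share of the deficit to be restored and no SD for PIO-PLA differences. Its own background offers no data on PIO at altitude and treats peripheral uptake as a possible main cause, not the only one.

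Recruitment stops at 8 on the strength of this figure. If the drug works partially, power may be well below 80%, and a reader told that the study had 80% power could take a non-significant result as evidence that PIO does not help at altitude.

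**Working it through.** **Inputs.** From Table 4, as delta ± spread, printed effect size, n:
- Row 1 (reference 4, exogenous oxidation): 0.35 ± 0.21, 1.11, 7
- Row 2 (reference 3, exogenous oxidation): 0.09 ± 0.06, 0.95, 8
- Row 3 (reference 3, MCR): 3.1 ± 2.0, 0.98, 7

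Assumed, because the documents do not say: alpha 0.05, one- or two-sided; a paired t test on one measure per arm; the same SD of within-volunteer differences for PIO-PLA as for SL-HA.

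**Formula.** Let d = mean within-volunteer difference / SD of those differences. Power is the probability that a noncentral t with n−1 degrees of freedom and noncentrality d√n passes the critical value. If PIO restores a share f of the deficit, d becomes f × d(SL-HA).

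**Step 1: the plan's own figure.** The smallest n for 80% power, rows 1/2/3, depends on how Table 4 is read. The printed effect sizes used as d give 7/9/8 one-sided and 9/11/11 two-sided. Delta/(±·√2), one-sided, gives 7/8/7, the printed values exactly. Delta/± gives 6/6/6 two-sided. So 8 is reproducible for SL-HA on a one-sided reading, and the arithmetic for that contrast is not the issue.

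**Step 2: Table 4's sample sizes at face value.** The d that gives 80% power:

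| | n=6 | n=7 | n=8 |
|---|---|---|---|
| Two-sided | 1.435 | 1.273 | 1.156 |
| One-sided | 1.186 | 1.067 | 0.978 |

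If 8 is the smallest sufficient n for row 2, its d lies between the n=8 and n=7 values. Eight completers then need f of at least 1.156/1.273 = 91% two-sided, or 0.978/1.067 = 92% one-sided. For rows 1 and 3, where 7 is the smallest sufficient n, d lies between the n=7 and n=6 values. The share needed is then 1.156/1.435 = 81% up to 91% two-sided, or 0.978/1.186 = 82% up to 92% one-sided.

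Power with 8 completers on the same basis:

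| Restoration | Row 2, two-sided | Row 2, one-sided | Rows 1 and 3, two-sided | Rows 1 and 3, one-sided |
|---|---|---|---|---|
| 75% | 56-64% | 59-65% | 64-74% | 65-73% |
| 50% | 29-34% | 35-39% | 34-42% | 39-45% |

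**Step 3: other readings of Table 4 (rows 1/2/3).**

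| d taken as | Sides | Share needed for 80%, n=8 | Power at half restoration |
|---|---|---|---|
| Printed effect size | two | 104/122/118% | 27.4/21.4/22.5% |
| Printed effect size | one | 88.1/103.0/99.8% | 41.0/33.3/34.7% |
| Delta/(±·√2) | two | 98.1/109.0/105.5% | 30.3/25.5/26.9% |
| Delta/(±·√2) | one | 83.0/92.2/89.2% | 44.4/38.6/40.3% |
| Delta/± | two | 69.4/77.1/74.6% | 52.8/44.9/47.2% |
| Delta/± | one | 58.7/65.2/63.1% | 68.3/60.5/62.9% |

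Over all readings the share needed runs from 59% to 122%, and half-restoration power from 21% to 68%.

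**Step 4: the SD assumption.** On the most favourable reading (delta/±), an SD 25% smaller for PIO-PLA raises half-restoration power to 77/68/71% two-sided and 88/82/84% one-sided. An SD 25% larger lowers it to 37/31/33% and 52/46/48%.

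**The case against.** The source contrast is disclosed: B5.8.1 names sea level and altitude, and Table 4 is labelled as coming from previous studies. The number 8 can be reproduced from it. Both points stand, so this is an unstated design assumption, not a slip in calculation.

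The percentages are conditional, and that also stands. A reader might take 91% as the threshold for the whole trial. It is the face-value bound for one row, two-sided; the rows that give 7 can need as little as 81%, and the most favourable reading 59%. Half restoration is a benchmark chosen here, not a target in the protocol. The SD comes from another contrast, and exogenous glucose oxidation will be analysed by a mixed model, not a paired t test.

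A reader might also infer that any partial drug effect would probably be missed. The figures do not support that: at 75% restoration, face-value power is above one half in every row.

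Finally, B2 is not the only statement of mechanism. The abstract (B1) is firmer and says the evidence suggests that reduced peripheral uptake is a primary factor. Even so, a primary factor is not the sole one, and neither section claims that PIO would abolish the deficit.

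**Conclusion.** The point holds: the 80% in B5.8.1 is not shown for the contrast under test. It applies to PIO versus PLA only if the drug restores all or most of the altitude deficit: at face value at least 91% (two-sided) or 92% (one-sided) for the limiting row, and about 81-91% or 82-92% for the other two. Face-value power at half restoration is 29-42% two-sided or 35-45% one-sided. With the SD unchanged, it stays below 80% on every reading of Table 4. Of the cases in Step 4, only delta/± with a one-sided test and an SD 25% smaller exceeds 80%.

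These figures assume alpha 0.05, a paired t benchmark and, except in Step 4, equal SDs for the two contrasts. The mismatch itself needs none of those assumptions.

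It is tempting to conclude that 8 is too few and that more volunteers are needed. The documents do not support that step, because they name no partial effect that the trial must detect and give no SD for it. What is wrong is the statement of power, not demonstrably the size.

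**What to change.** In B5.8.1, replace the power sentence with one about the tested contrast:

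> *Eight completers give 80% power (test, alpha and sides as used) to detect a PIO-versus-PLA difference of [x] in exogenous glucose oxidation and [y] in MCR, equal to [z]% of the SL-HA difference in Table 4, assuming the same SD of within-volunteer differences; smaller effects may be missed.*

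The sponsor should fill x, y and z from the SD of within-volunteer differences that it used. As an illustration only: if the ± column is that SD and the test is two-sided, the detectable differences are 1.156 × 0.21 = 0.243 (69% of 0.35), 1.156 × 0.06 = 0.069 (77% of 0.09) and 1.156 × 2.0 = 2.31 (75% of 3.1), in Table 4's units.

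In B5.2.2, reword the reason for 8 to match. In B5.8.2, add that the PIO-PLA difference will be reported with a 95% confidence interval.

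The cost is wording and a less favourable stated figure. The number of completers stays at 8; enrolling more is not part of this fix.

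### Table 4's Delta, effect-size and sample-size columns do not follow from one another, so the 80% power statement for 8 completers is not supported by the effect sizes the plan prints

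*Combined protocol and SAP*

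**What the plan says.** Section B5.8.1 gives the sample size in one sentence, which opens "Based on results of exogenous carbohydrate oxidation and MCR rate between SL and HA in our previous investigation" and concludes that "a sample size of 8 is required to achieve 80% power". The support is "Table 4: Previous study effect sizes", with three rows:

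| Row | Delta | Effect size | n |
|---|---|---|---|
| 1. Exogenous glucose oxidation (ref. 4) | 0.35 ± 0.21 | 1.11 | 7 |
| 2. Exogenous glucose oxidation (ref. 3) | 0.09 ± 0.06 | 0.95 | 8 |
| 3. Metabolic clearance rate (ref. 3) | 3.1 ± 2.0 | 0.98 | 7 |

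The section does not give alpha, sidedness, the test, the meaning of ±, the definition of the effect size or a within-person correlation.

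Section B5.2.2 ties recruitment to the figure. It begins "To complete testing on the 8 volunteers necessary to reach statistical power" and adds that "All screening will stop once complete data has been collected on 8 volunteers".

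On analysis, B5.8.2 says "Paired T tests will be used to assess effects of study arms (HA+PIO vs. HA+PLA") for a list of outcomes that does not include exogenous glucose oxidation. For that outcome, "Mixed Model repeated measures ANOVA will be used to assess the effects of condition, time, and their interactions". Hypothesis 1 in B4 is directional: exogenous glucose oxidation, Rd and MCR "will be greater after PIO administration compared to PLA".

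**The concern.** In a crossover the natural effect size is the mean within-person difference divided by the SD of those differences. If Delta ± is a mean and SD of differences, the effect-size column should be the ratio of the two numbers beside it. It is about two thirds of that ratio in every row. The next step fails as well: the listed effect sizes, put through a paired t-test at the usual 5% level, do not return the listed sample sizes.

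This matters because 8 complete data sets is the point at which screening ends, and the 80% figure is the only statistical reason given for it. A null PIO-PLA result will be read against that figure. The table concerns a different contrast, so it does not tell the reader what PIO-PLA difference 8 volunteers could detect.

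**Working it through.** **Inputs.** Delta, ±, effect size and n come from Table 4, and the 80% target from B5.8.1. The plan states no alpha or sidedness; I assume 0.05 and show both one- and two-sided results. The paired t-test is assumed from the crossover design.

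**Step 1: Delta to effect size.**

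| Row | Delta/± | Range allowed by rounding | Listed | Delta/± ÷ listed |
|---|---|---|---|---|
| 1 | 0.35/0.21 = 1.67 | 1.60–1.73 | 1.11 | 1.50 |
| 2 | 0.09/0.06 = 1.50 | 1.31–1.73 | 0.95 | 1.58 |
| 3 | 3.1/2.0 = 1.55 | 1.49–1.62 | 0.98 | 1.58 |

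No listed value lies in its range. This step does not depend on alpha or sidedness.

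If ± is instead the SD within each condition, the paired effect is Delta/(±√(2(1−ρ))). Solving for the within-person correlation gives ρ = 1 − (Delta/±)²/(2 × ES²), which is −0.13, −0.25 and −0.25. At ρ = 0 the effect is Delta/(±√2) = 1.18, 1.06 and 1.10, with rounding ranges 1.13–1.22, 0.92–1.22 and 1.05–1.14. Only row 2's range contains its listed value.

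**Step 2: effect size to n.** For a paired effect d, T is noncentral t with n − 1 df and noncentrality d√n. Power is the probability that T exceeds the critical value, and the required n is the smallest that gives 80%. Example, row 2 at n = 8: noncentrality 0.95 × √8 = 2.69 on 7 df, giving power 0.637 two-sided and 0.780 one-sided.

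| Reading | Test | n needed, rows 1–3 | Power at n = 8 |
|---|---|---|---|
| Printed in the plan | not stated | 7, 8, 7 | 80% claimed |
| Listed effect sizes as paired | two-sided 0.05 | 9, 11, 11 | 77%, 64%, 66% |
| Listed effect sizes as paired | one-sided 0.05 | 7, 9, 8 | 88%, 78%, 80% |
| Delta/± as paired | two-sided 0.05 | 6, 6, 6 | 98%, 95%, 96% |
| Delta/(±√2) | one-sided 0.05 or two-sided 0.10 | 7, 8, 7 | 91%, 85%, 87% |
| Delta/(±√2) | two-sided 0.05 | 8, 10, 9 | 81%, 73%, 76% |

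Rounding leaves 9, 11, 11 unchanged. It allows 8 or 9 for row 3 in the one-sided line, and 5–6, 5–7 and 6 in the Delta/± line.

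I also tried the listed effect sizes, as paired, at every alpha from 0.005 to 0.30 in steps of 0.0005, one- and two-sided. None returns 7, 8, 7. Delta/± returns 7, 8, 7 at a two-sided alpha of about 0.021 to 0.024. Every route found to the printed n therefore sets the printed effect sizes aside.

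**Step 3: what 8 completers can detect.** Solving for 80% power at n = 8 gives d = 1.16 (two-sided 0.05, 7 df) or 0.98 (one-sided 0.05, 7 df). If a period term leaves 6 df, the two-sided value is about 1.19.

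To put 1.16 on the scale of Table 4, assume that PIO-PLA differences have the same SD as the sea level-altitude differences. If ± is the SD of differences, 1.16 SDs is 1.16/1.67, 1.16/1.50 and 1.16/1.55, or 69%, 77% and 75% of Delta. If the listed effect sizes are the paired ones, it is 1.16/1.11, 1.16/0.95 and 1.16/0.98, or about 104%, 122% and 118% of Delta.

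**The case against.** The strongest reply is that this is missing specification more than wrong arithmetic. The plan never says that ± is the SD of paired differences or that the effect size is Delta/±, and the earlier studies that could settle it are not at hand. The printed 7, 8, 7 can be recovered with Delta/(±√2), a condition SD with no within-person correlation. That reading does not even require a one-sided test: two-sided alpha of 0.10 gives the same answer and suits an ANOVA F-test. Under it, 8 completers have 85–91% power.

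Much of this stands. It rules out two stronger conclusions that a reader might draw. One is that the trial is underpowered, or needs 11 volunteers. The documents do not show that, because two-sided 0.05 power at n = 8 lies well above 80% if ± is the SD of differences. The other is that the columns cannot be reconciled under any reading. That is not shown either, since a definition the plan does not give could exist, and row 2 alone is compatible with a condition SD once rounding is allowed.

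What does not stand is that the recovery rescues the 80% statement. It uses effect sizes of 1.18, 1.06 and 1.10 in place of those printed, and relies on an alpha or sidedness that the plan does not declare. The direction of Hypothesis 1 is not a declaration of a one-sided test; at one-sided 0.05 the listed 0.95 still gives 78% at n = 8.

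A fair caution also applies to 1.16. It assumes complete data and a within-person contrast on 7 df, and B5.8.2 does not specify the mixed model closely enough to guarantee that.

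**Conclusion.** The point holds in a limited form and should be fixed. The 80% power statement does not follow from the effect sizes the plan prints. Delta/± exceeds the listed effect size by a factor of 1.50 to 1.58, and the listed values as paired effects return 9, 11, 11 (two-sided 0.05) or 7, 9, 8 (one-sided 0.05), never 7, 8, 7. The row that determines n = 8 misses 80% at the 5% level either way, at 64% or 78%. A shortfall at n = 8 is not proven, because other unstated readings give 85% to 98%.

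The Delta-to-effect-size gap rests only on the table's figures and on reading the effect size as Delta/±. The n and power figures rest on a paired t-test and the alpha shown.

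Separately, the table's effects are sea level versus altitude. Carrying them over to PIO versus PLA assumes a drug effect as large as the altitude effect, with the same variability. The plan states no PIO-PLA difference, so this is an open assumption and not an arithmetic error.

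**What to change.** Keep n = 8. In Table 4, define ± and the effect size, and correct the entries so that Delta ±, effect size and n follow from one stated definition, alpha and sidedness. If a condition SD was used, give the within-person correlation.

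Then replace the 80% statement in B5.8.1 with one of two things:

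- the power at n = 8 for the corrected paired effect; or
- the detectable difference, worded along these lines: with 8 volunteers with complete data and a within-person PIO-PLA contrast on 7 df, a two-sided 0.05 test has 80% power for a mean difference of 1.16 SDs of the paired differences. Use 0.98 if a one-sided 0.05 test is declared, or about 1.19 (two-sided) if a period term leaves 6 df.

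Say in either case that Table 4 describes sea level versus altitude. Do not insert 64–77% as the power unless the listed values are confirmed as paired effect sizes tested two-sided at 0.05.

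The cost is a table correction and a sentence, with no added volunteers. The downside for the sponsor is that the stated power may become less favourable, and that declaring a two-sided test raises the detectable difference from 0.98 to 1.16 SDs.
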